## 7 Reporting and Documentation of Results

### 7.1 Evaluation of efficacy (or Activity)

#### 7.1.1 Definitions

##### Evaluable for toxicity

All patients will be evaluable for toxicity from the time of [F]F-AraG administration.

### 7.2 Evaluation of Safety

Analyses will be performed for all patients receiving the radiotracer. The study will use the [CTCAE v4.0](#) for reporting of adverse events.

### 7.3 Definition of Adverse Events

#### 7.3.1 Adverse Event

An adverse event (also known as an adverse experience) is defined as any untoward medical occurrence associated with the use of a drug in humans, whether or not considered drug related. More specifically, an adverse event (can be any unfavorable and unintended sign (e.g., an abnormal laboratory finding), symptom, or disease temporally associated with the use of a drug, without any judgment about causality. An adverse event can arise from any use of the drug (e.g., off-label use, use in combination with another drug) and from any route of administration, formulation, or dose, including an overdose.

#### 7.3.2 Adverse Reaction

An adverse reaction is defined as any adverse event caused by the use of a drug. Adverse reactions are a subset of all suspected adverse reactions for which there is reason to conclude that the drug caused the event.

##### 7.3.2.1 Suspected

A suspected adverse reaction is defined as any adverse event for which there is a reasonable possibility that the drug caused the adverse event. For the purposes of IND safety reporting, "reasonable possibility" indicates that there is evidence to suggest a causal relationship between the drug and the adverse event. A suspected adverse reaction implies a lesser degree of certainty about causality than an adverse reaction.

##### 7.3.2.2 Unexpected

An adverse event or suspected adverse reaction is considered *unexpected* if it is not listed in the investigator brochure or package insert(s), or is not listed at the specificity or severity that has been observed, or, if an investigator brochure is not required or available, is not consistent with the risk information described in the general investigational plan or elsewhere in the current application.

“Unexpected,” as used in this definition, also refers to adverse events or suspected adverse reactions that are mentioned in the investigator brochure as occurring with a class of drugs or as anticipated from the pharmacological properties of the drug, but are not specifically mentioned as occurring with the particular drug under investigation.

Adverse events that would be anticipated to occur as part of the disease process are considered *unexpected* for the purposes of reporting because they would not be listed in the investigator brochure. For example, a certain number of non-acute deaths in a cancer trial would be anticipated as an outcome of the underlying disease, but such deaths would generally not be listed as a suspected adverse reaction in the investigator brochure.

### 7.3.2.3 Serious

An adverse event or suspected adverse reaction is considered *serious* if, in the view of either the investigator or sponsor, it results in any of the following outcomes:

- Death
- Life-threatening adverse event
- Inpatient hospitalization or prolongation of existing hospitalization
- A persistent or significant incapacity or substantial disruption of the ability to conduct normal life function
- Congenital anomaly/birth defect

Important medical events that may not result in death, are life-threatening, or require hospitalization may be considered serious when, based upon appropriate medical judgment, they may jeopardize the patient or subject and may require medical or surgical intervention to prevent one of the outcomes listed in this definition. Examples of such medical events include allergic bronchospasm requiring intensive treatment in an emergency room or at home, blood dyscrasias or convulsions that do not result in inpatient hospitalization, or the development of drug dependency or drug abuse.

### 7.3.2.4 Life-threatening

An adverse event or suspected adverse reaction is considered life-threatening if, in the view of either the investigator or sponsor, its occurrence places the patient or subject at immediate risk of death. It does not include an adverse event or suspected adverse reaction that, had it occurred in a more severe form, might have caused death.

## 7.4 Recording of an Adverse Event

All grade 3 and above adverse events will be recorded using the NCI CTCAE v4.0. The Investigator will assign attribution of the possible association of the event with use of the investigational drug.

Relationship	Attribution	Description
Unrelated to investigational drug/intervention	Unrelated	The AE is clearly NOT related to the intervention
	Unlikely	The AE is doubtfully related to the intervention
Related to investigational drug/intervention	Possible	The AE may be related to the intervention
	Probable	The AE is likely related to the intervention
	Definite	The AE is clearly related to the intervention

Signs or symptoms reported as adverse events will be graded and recorded by the Investigator according to the CTCAE. When specific adverse events are not listed in the CTCAE they will be graded by the Investigator as *none, mild, moderate* or *severe* according to the following grades and definitions:

- Grade 0 No AE (or within normal limits)
- Grade 1 Mild; asymptomatic or mild symptoms; clinical or diagnostic observations only; intervention not indicated
- Grade 2 Moderate; minimal, local, or noninvasive intervention (e.g., packing, cautery) indicated; limiting age-appropriate instrumental activities of daily living (ADL)
- Grade 3: Severe or medically significant but not immediately life-threatening; hospitalization or prolongation of hospitalization indicated; disabling; limiting self-care ADL
- Grade 4: Life-threatening consequences; urgent intervention indicated
- Grade 5: Death related to AE

## 7.5 Follow-up of Adverse Events

All adverse events will be followed with appropriate medical management until resolved. Patients removed from study for unacceptable adverse events will be followed until resolution or stabilization of the adverse event. For selected adverse events for which administration of the investigational drug was stopped, a re-challenge of the subject with the investigational drug may be conducted if considered both safe and ethical by the Investigator.

## 7.6 Expedited Reporting

### **Reporting to the Data and Safety Monitoring Committee**

If a death occurs during the treatment phase of the study or within 30 days after the last administration of the study drug(s) and it is determined to be related either to the study drug(s) or to a study procedure, the Investigator or his/her designee must notify the DSMC Chair (or qualified alternate) within 1 business day of knowledge of the event. The contact may be by phone or e-mail.

### **Reporting to UCSF Institutional Review Board**

The Principal Investigator must report events meeting the UCSF IRB definition of “Unanticipated Problem” (UP) within 10 business days of his/her awareness of the event.

### **Expedited Reporting to the Food and Drug Administration**

If the study is being conducted under an IND, the Sponsor-Investigator is responsible for determining whether or not the suspected adverse reaction meets the criteria for expedited reporting in accordance with Federal Regulations (21 CFR §312.32).

The Investigator must report in an IND safety report any suspected adverse reaction that is both serious and unexpected. The Sponsor-Investigator needs to ensure that the event meets all three definitions:

- Suspected adverse reaction (as defined in 7.3.2.1)
- Unexpected (as defined in 7.3.2.2)
- Serious (as defined in 7.3.2.3)

If the adverse event does not meet all three of the definitions, it should not be submitted as an expedited IND safety report.

The timeline for submitting an IND safety report to FDA is no later than **15 calendar days** after the Investigator determines that the suspected adverse reaction qualifies for reporting (21 CFR 312.32(c)(1)).

Any unexpected fatal or life-threatening suspected adverse reaction will be reported to FDA no later than **7 calendar days** after the Investigator's initial receipt of the information (21 CFR 312.32(c)(2)).

Any relevant additional information that pertains to a previously submitted IND safety report will be submitted to FDA as a Follow-up IND Safety Report without delay, as soon as the information is available (21 CFR 312.32(d)(2)).

## **8 Statistical Considerations and Image Analysis**

### **8.1 Image Processing and Analysis**

Trained nuclear medicine physicians and molecular imaging scientists will evaluate the reconstructed PET, PET/MR images using a PET volume computer-assisted reading software package. Volumetric regions of interest will be chosen around tumors based on anatomic (MR) images and activity within the tumor will be expressed in a standardized uptake value (SUV) format where SUV will be defined as [concentration of tracer in tumor]/(injected dose/body weight). Tumor SUV at baseline (before anti-PD-1 or anti-PD-L1 treatment) will be compared with the post-therapy values to determine the change in SUV associated with the therapy. Whole body images will be analyzed to determine differences in tracer distribution relative to pre/post therapy and versus the normal subject pool already studied.

### **8.2 Sample Size Determination**

The sample size determination is based on the primary endpoint of the study, the change between pre-treatment and post-treatment  $SUV_{max}$  in the primary and/or metastatic tumor(s) and on [ $^{18}F$ ]F-AraG PET/MR imaging. The null hypothesis is that post-treatment  $SUV_{max}$  increases by at least 2-fold compared to baseline  $SUV_{max}$  in 1% patients. The alternative hypothesis is that post-treatment  $SUV_{max}$  increases by at least 2-fold compared to baseline  $SUV_{max}$  in 20% patients. For the SOC cohort (Cohort 2), a Simon's two-stage design will be used. Eight patients will be accrued

initially, if no patient is observed to have a post-treatment  $SUV_{max}$  that increases by at least 2-fold compared to baseline  $SUV_{max}$ , the study will be halted; otherwise, an additional 11 patients will be accrued. The null hypothesis will be rejected if 2 or more of the 19 patients are observed to have at least a 2-fold increase in post-treatment  $SUV_{max}$  compared to baseline  $SUV_{max}$ . This design yields a type I error rate of 0.05 and power of 80%. For the neoadjuvant cohort (Cohort 1), one-stage design will be applied with 12 patients accrued to ensure 80% power at a significance level of 0.05.

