### 3.2 Number of Subjects

A total of 31 patients will be enrolled over an accrual period of approximately 20 months. Twelve (12) patients will be enrolled in the neoadjuvant atezolizumab cohort, and 19 patients will be enrolled in the SOC anti-PD-1 or anti-PD-L1 cohort.

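### Cohort 1 (12 patients, one stage) cannot have both 80% power and a 0.05 significance level: the best valid cutoff gives 72.5%

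*Combined protocol and SAP*

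**What the plan says.** Section 8.2 bases the sample size on the primary endpoint, the change in tumour SUVmax. Before separating the cohorts it sets one pair of hypotheses: SUVmax at least doubles in 1% of patients under the null and "in 20% patients" under the alternative.

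- **Cohort 2 (standard of care)** has a full Simon rule: 8 patients first, stop if none responds, otherwise continue to 19. The decision rule is explicit: "The null hypothesis will be rejected if 2 or more of the 19 patients are observed" to have the 2-fold rise. The section then states: "This design yields a type I error rate of 0.05 and power of 80" per cent.
- **Cohort 1 (neoadjuvant)** gets one sentence: a "one-stage design will be applied with 12 patients accrued to ensure 80% power at a significance level of 0.05". There is no cutoff, sidedness or formula.

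Section 3.2 repeats the number: "Twelve (12) patients will be enrolled in the neoadjuvant atezolizumab cohort". Section 8.4 confines the interim look to Cohort 2. Section 3.5 replaces patients who leave before the second scan, so 12 evaluable patients is the intended figure.

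**The concern.** With 12 patients and a null rate of 1%, only 0.12 responders are expected under the null, so the attainable type I error moves in large steps from one cutoff to the next. A design that meets two targets at a given n then has to be checked cutoff by cutoff. The plan names no cutoff for Cohort 1, so its claim cannot be read off the page.

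The missing cutoff matters most when exactly one of 12 patients responds, which has probability 0.206 at a true rate of 20%. That result is positive under a cutoff of 1 and negative under a cutoff of 2. If the analyst settles this after seeing the data, either choice contradicts a stated property of the design. A negative Cohort 1 result would also be read as carrying a 20% chance of having missed a true effect, when the valid rule misses 27.5%. Cohort 1 is the only cohort with post-treatment surgical pathology, so its result is likely to be leaned on.

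**Working it through.** **Inputs.** n = 12, one stage; p0 = 0.01; p1 = 0.20; significance level 0.05; power 0.80 (all Section 8.2). No interim look (Section 8.4) and no dropout allowance (Section 3.5).

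**Check of the method on Cohort 2.** Stop at 0 of 8, then reject at 2 or more of 19:

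P(reject) = P(X₁ ≥ 2) + P(X₁ = 1) × P(X₂ ≥ 1), with X₁ ~ Bin(8, p) and X₂ ~ Bin(11, p).

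- p = 0.20: 0.4967 + 0.3355 × 0.9141 = 0.8034. The stated 80% is reproduced.
- p = 0.01: 0.0027 + 0.0746 × 0.1047 = 0.0105. The stated 0.05 is not what the rule yields; the actual value is about one fifth of it. The rule would stay within 0.05 up to a null rate of about 2.3%.

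**Cohort 1.** With X ~ Bin(12, p):

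- P(X ≥ 1) = 1 − (1 − p)¹²
- P(X ≥ 2) = 1 − (1 − p)¹² − 12p(1 − p)¹¹

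At p = 0.01: (0.99)¹² = 0.8864 and 12 × 0.01 × (0.99)¹¹ = 0.1074.
At p = 0.20: (0.80)¹² = 0.0687 and 12 × 0.20 × (0.80)¹¹ = 0.2062.

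| Reject if responders in 12 | Type I error | Power at 20% |
|---|---|---|
| ≥ 1 | 0.1136 | 0.9313 |
| ≥ 2 | 0.0062 | 0.7251 |
| ≥ 3 | 0.0002 | 0.4417 |

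Only the first row reaches 80% power, and its type I error is more than twice 0.05. The least strict cutoff that respects 0.05 is 2 or more, with type II error 1 − 0.7251 = 0.275. Sidedness does not matter: 0.0062 also passes 0.025, and 0.1136 fails both.

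**How far off.** Solving P(X ≥ 2) = 0.80 at n = 12 gives a true rate of about 23.0%. Keeping 1% versus 20%, n = 13 with cutoff 2 has power 0.7664. The smallest n meeting both targets is 14 (cutoff 2: type I error 0.0084, power 0.8021).

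**Other readings.**

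- *Two-stage in Cohort 1.* The Abstract mentions a Simon design without limiting it to a cohort. A futility stop within 12 patients can only remove rejections from the cutoff-2 rule, so power cannot exceed 72.5%. With a final cutoff of 1 and a stop at 0 responders, the first stage can have at most 5 patients before the type I error passes 0.05 (0.049 at 5), and power is then 0.6723.
- *Continuous test.* Section 8.5 lists a paired Wilcoxon signed-rank test, but the plan gives no effect size or SD from which 80% power could be derived.
- *Approximations.* The plain normal formula gives n = 6.93 one-sided and 7.83 two-sided. The one-sided continuity-corrected normal gives 11.60 and the one-sided arcsine 11.70; both round up to 12.

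**The case against.** Four points can be made for the plan.

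1. **The number 12 has a plausible source.** Two standard one-sided approximations round up to it. That probably explains the figure, but both are unreliable with 0.12 expected null responders, and no count rule achieves the power they imply. A randomised exact test at 0.05 would reach 80.9%, but it has no fixed cutoff and the plan does not mention one.
2. **The significance level already selects the cutoff.** An analyst who holds to 0.05 must use 2 or more of 12. This is fair, and it limits the room for choice after the fact. It does not remove it, because that analyst must then abandon the stated power, and the plan does not say which property gives way.
3. **Little depends on the figure.** The study is a pilot, Section 2.2.1 words the primary endpoint descriptively, Section 8.5 contains no responder-count test, and Cohort 1 has no go/no-go rule. The shortfall is 7.5 percentage points, or two patients. All of this limits the consequence, but Section 8.2 still makes an explicit power claim on the primary endpoint, and the claim is false.
4. **For Cohort 2, 0.05 can be read as a ceiling.** On that reading the rule is valid and conservative, and no decision changes. That stands. The sentence, however, says what the design yields, and it yields 0.0105.

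**Conclusion.** The Cohort 1 claim is wrong as written. At the plan's own rates of 1% and 20%, 12 patients in one stage give 72.5% power at the best cutoff that keeps the type I error within 0.05, not 80%. The only cutoff with at least 80% power has a type I error of 11.4%. The Cohort 2 power is right, but its type I error is overstated at 0.05 against an exact 0.0105; that error is harmless in direction.

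This rests on two assumptions: the single pair of hypotheses in Section 8.2 applies to Cohort 1 (no other is given), and all 12 patients are evaluable. Fewer evaluable patients would lower the power at that cutoff further.

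**What to change.** Rewrite the last two sentences of Section 8.2.

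- **Cohort 1:** delete the claim "to ensure 80% power" "at a significance level of 0.05" and put in its place: *H0 is rejected when at least 2 of 12 patients show a 2-fold or greater SUVmax increase; exact type I error 0.006; power 72.5% at a true rate of 20%, and 80% at a true rate of about 23%.*
- **Cohort 2:** replace the stated operating characteristics with: *exact type I error 0.0105, power 80.3%.*

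The cost is protocol wording only. No patients are added, and the one unwelcome effect is a lower stated power for Cohort 1. If the sponsor prefers to keep 80% power at a true rate of 20%, Cohort 1 needs 14 patients with the same cutoff of 2, and the total of 31 would become 33 wherever it appears. The correction itself does not require that.

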### 8.3 Accrual Estimates

The anticipated accrual rate is approximately 1-2 patients per month, leading to an estimated total accrual period of 20 months. Twelve (12) patients are anticipated to be enrolled in the neoadjuvant atezolizumab cohort, and 19 patients are anticipated to be enrolled in the SOC anti-PD-1 or anti-PD-L1 cohort. A total of 31 patients will be accrued.

### 8.4 Interim Analysis and Safety Stopping Rule

Interim analysis will be performed only for the SOC cohort (Cohort 2). After 8 patients are imaged at both baseline and post-treatment time points, the acquired PET/MR imaging results will be reviewed. If the post-treatment  $SUV_{max}$  increases by at least 2-fold compared to baseline  $SUV_{max}$  for at least one patient, the study will continue accrual for a total of 19 patients. If no patient is observed to have a post-treatment  $SUV_{max}$  that increases by at least 2-fold compared to baseline  $SUV_{max}$ , the study will be halted and the imaging protocol re-evaluated, with particular attention to the post-treatment imaging time point. Subsequently, the scan results will be analyzed on a continuous basis, and accrual may be halted to adjust imaging parameters on an as needed basis.

Complete safety data will also be analyzed at the time of interim analysis. Accrual will be halted after one serious adverse reaction attributable to [ $^{18}F$ ]F-AraG is seen. If Grade 3 or higher toxicities are observed in more than 20% of all patients accrued which are attributable to [ $^{18}F$ ]F-AraG, the study will be stopped and the dose of the of [ $^{18}F$ ]F-AraG reexamined.

### 8.5 Analytic Plan

The median and interquartile range of  $SUV_{max}$  within the tumor and lymphoid tissues across all patients will be descriptively reported for baseline (before treatment) and post-treatment images, separately. The nonparametric paired Wilcoxon Signed-rank test will be used to assess differences in  $SUV_{max}$  before and after treatment. The log2 ratio of post-treatment versus baseline  $SUV_{max}$  within the tumor and lymphoid tissues will also be calculated.

To correlate change in  $SUV_{max}$  to clinical and/or pathologic response, patients will be divided into two groups: those who achieved clinical response and/or pathologic down-staging, and those who did not. The median and interquartile range of change in  $SUV_{max}$  from baseline to pre-surgery in the different groups will be descriptively reported. For Cohort 1, clinical response will be determined by abdominal imaging performed  $\leq 30$  days after the last dose of atezolizumab prior to cystectomy compared to baseline pre-treatment imaging using RECIST v1.1 criteria, as specified in the companion treatment protocol (CC# 14524). For Cohort 1, pathologic response will be determined by evidence of down-staging (e.g. from muscle invasive to non-muscle invasive, or complete pathologic response) at the time of cystectomy.

Immunohistochemistry for immune infiltration will be performed in the [name] lab ([name] L et al. J

Natl Cancer Inst 2014). Briefly, 5-micron FFPE slides from archival tumor tissue or cystectomy tissue will be used for staining. For double stains, slides will first be incubated with antibody to CD8 and visualized with horseradish peroxidase using DAB+, followed by incubation with antibody to CD3 and visualized with alkaline phosphatase using Permanent Red. Tissues will be counterstained with hematoxyclin before analysis. Automatic cell counts for single- and double-stained cells will be determined using the Axiovision software (Zeiss, Peabody, MA). The correlation between change from baseline to post-treatment  $SUV_{max}$  on [ $^{18}F$ ]F-AraG PET and CD3+ and CD3+CD8+ immune infiltration ( $\#/\mu m^2$ ) by IHC will be determined using Spearman's  $\rho$  statistic, separately.

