## 2.2 Endpoints

### 2.2.1 Primary Endpoint

To describe the change between pre-treatment and post-treatment maximum standardized uptake values ( $\text{SUV}_{\text{max}}$ ) in the primary and/or metastatic tumor(s) on whole-body [ $^{18}\text{F}$ ]F-AraG PET/MR imaging by study cohort.

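### The analytic plan never analyses the 2-fold count on which both cohorts are sized, and its only pre/post test has no stated role

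*Combined protocol and SAP*

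**What the plan says.** - **Section 2.2.1 (Primary Endpoint)** is descriptive and asks for results by study cohort: "To describe the change between pre-treatment and post-treatment maximum standardized uptake values". It names neither a 2-fold criterion nor a test.
- **Section 8.2 (Sample Size Determination)** states its hypotheses as the share of patients with at least a 2-fold rise in SUVmax: 1% under the null, 20% under the alternative. Cohort 2 is a Simon two-stage design. "Eight patients will be accrued" first, and accrual halts if none of them doubles; "otherwise, an additional 11 patients will be accrued". The final rule is: "The null hypothesis will be rejected if 2 or more of the 19 patients are observed to have at least a 2-fold increase". Type I error is given as 0.05 and power as 80%. Cohort 1 is a one-stage design with 12 patients and the same stated error rates, but no cut-off.
- **Section 8.4 (Interim Analysis and Safety Stopping Rule)** uses the same count at 8 patients in Cohort 2.
- **Section 8.5 (Analytic Plan)** reports the median and IQR of SUVmax for each time point separately, over all patients together. It then states: "The nonparametric paired Wilcoxon Signed-rank test will be used to assess differences in" SUVmax before against after treatment. A log2 post/baseline ratio is to be calculated, with no summary or use specified. The doubling count does not appear.

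**The concern.** The two analyses answer different questions. The count asks whether a minority of patients at least doubles. The signed-rank test asks whether paired changes are shifted from zero. A few doublers need not shift the whole group, and a small rise in everyone need not produce one doubler.

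Anyone following 8.5 literally would never compute the quantity that 8.2 tests. An unlabelled p-value would also stand beside a count rule, and readers could not tell which is the primary result. The power statement would be read as covering the 8.5 test, which it does not. The doubling rate and its uncertainty are also what later trials need from a pilot study, and the plan provides for no estimate or interval.

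**Working it through.** **1. The plan's own figure, Cohort 2.** Inputs from 8.2: p = 0.01 or 0.20; 8 patients, then 11 more; continue with at least 1 of 8; reject with at least 2 of 19.

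P(reject) = P(X1 = 1) × P(X2 ≥ 1) + P(X1 ≥ 2), with X1 ~ Bin(8, p) and X2 ~ Bin(11, p).

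- p = 0.20: 0.3355 × 0.9141 + 0.4967 = 0.803. The stated 80% reproduces.
- p = 0.01: 0.0746 × 0.1047 + 0.0027 = 0.0105. The stated 0.05 is the design limit, not the attained level.

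Both figures describe the count rule only.

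**2. Cohort 1, n = 12.** No cut-off is stated, so try the two candidates.

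- 2 or more: power = 1 − 0.8^12 − 12 × 0.2 × 0.8^11 = 1 − 0.0687 − 0.2062 = 0.725; alpha = 1 − 0.99^12 − 12 × 0.01 × 0.99^11 = 0.006.
- 1 or more: power = 1 − 0.8^12 = 0.931; alpha = 1 − 0.99^12 = 0.114.

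Neither gives 80% power with alpha at or below 0.05. With 2 or more as the cut-off, 14 patients would give 0.802.

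**3. How often the analyses disagree in Cohort 2.** The 8.2 alternative fixes only the doubling rate, 20%. The signed-rank result depends on the other 80% of patients, so their behaviour has to be assumed. The figures come from 20,000 to 40,000 simulated trials per setting, with an exact signed-rank test at 0.05 on all 19 patients.

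| Assumption about the other patients | Disagreement |
|---|---|
| Unchanged on average, two-sided test | about 50–59% |
| Unchanged on average, one-sided test | about 44–51% |
| Rise to a median 1.1- to 1.15-fold (ln-noise SD 0.2, two-sided) | about 21–26% |
| Rise, mean log2 ratio +0.2 (SD 0.3) | about 20–21% |
| Fall to 0.9-fold | about 77% |
| Fall, mean log2 ratio −0.2 or −0.3 | about 76–85% |
| All patients from one normal distribution of log2 ratios, SD 0.25–0.5 | about 20% |
| The same, SD 0.75 / 1.0 / 1.19 | 28–42% / 57–73% / 68–79% |

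Three notes on reading the table:

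- The low end is largely the count rule missing its own alternative: 1 − 0.803 = 0.197 when the signed-rank test is almost always significant.
- The 85% counts a significant fall as a signed-rank finding. In that setting the rule rejects in 80.1% of trials and a significant rise occurs in 0.3%, so disagreement is at most about 80% if only rises count.
- The low end of the first row includes settings where noise pulls the observed doubling rate below 20% (16.3% in one).

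For Cohort 1, with an assumed cut-off of 2 or more, the range is 27–84%.

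**4. Power of the signed-rank test.** With the other patients unchanged, a two-sided test finds a rise in about 25–31% of trials, against 70–81% for the rule. If 20% rise 3-fold and the rest rise 1.1-fold, it is 82% against 79–80%; at 1.15-fold, 95% against 80%. The order can go either way.

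**5. Estimating the rate in Cohort 2.** The futility stop biases the simple proportion.

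- Mean at p = 0.2: [8 × 0.2 + 11 × 0.2 × (1 − 0.8^8)] / 19 = (1.6 + 2.2 × 0.8322) / 19 = 0.181.
- At exactly 2 of 19 the simple proportion is 10.5% (naive exact 95% interval 1.3–33.1%). The two-stage unbiased estimate is (11 + 7) / (88 + 28) = 18/116 = 15.5%. Its exact interval, ordering a stage-1 stop below every stage-2 total, is 1.6–38.6%.

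**The case against.** The strongest reply is that Cohort 2 already has a rule. Section 8.2 says in terms when the null is rejected, 8.4 uses the same count, and 8.5 gives the signed-rank test no hypothesis or success criterion. A reader might infer from 8.5 that nothing decides which result counts. For Cohort 2 the documents do not support that: a signed-rank p-value cannot reject the 8.2 null. What stands is that 8.5 neither carries the rule over nor gives the test a role, and that Cohort 1 has no cut-off at all.

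A reader might also infer that the analyses conflict in about half of trials under the plan's own alternative, or that the signed-rank test has far less power. Both follow if the other 80% of patients are taken as unchanged on average, which the plan never says. Other assumptions give about 20% or about 80%, and the power order can reverse.

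Trials halted at 8 patients have no 19-patient data set. Testing those on their 8 patients lowers disagreement: from 26% to 17% in the 1.1-fold case, and to about 11% in the lowest setting found. The signed-rank sentence names no cohort. Pooled over all 31 patients, the test would be significant in 38–46% of trials in the unchanged scenario.

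The log2 ratio in 8.5 does link the sections, since a value of 1 or more is exactly a doubling. But the plan says only that it is calculated. Finally, this is a pilot with a descriptive endpoint, and the estimation bias at a true 20% is 1.9 percentage points. That bears on severity; the mismatch remains.

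**Conclusion.** The point holds in a limited form. Both cohorts are sized on a doubling proportion that the analytic plan never analyses. The one pre/post test it names addresses another hypothesis, has no stated role, and is not covered by the 80% power. Section 8.5 also summarises all patients together where 2.2.1 asks for results by cohort.

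For Cohort 2 this is a failure to carry a defined rule forward. For Cohort 1 it is a real gap: the test the cohort was sized on cannot be run without a cut-off, and no cut-off at n = 12 meets the stated error rates under an exact binomial test.

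The two analyses can disagree often, but no single rate can be attributed to the plan. The roughly 20% to 85% range rests on assumed behaviour of the patients who do not double and on the test's sidedness, and it is lower if halted trials are tested on 8 patients. The correction should be made before the data are analysed, but the point does not invalidate the design.

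**What to change.** Amend 8.5, by cohort:

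- **Primary analysis:** the number and proportion of patients with a post/baseline SUVmax ratio of 2 or more (log2 ratio of 1 or more).
- **Cohort 2:** apply the 8.2 rule; report a two-stage estimate with an exact two-stage 95% interval.
- **Cohort 1:** state the cut-off and report the proportion with an exact interval. If the cut-off is 2 or more of 12, restate the operating characteristics as alpha 0.006 and power 72.5%.
- **Signed-rank test:** label it supportive, give its alpha, sidedness and cohort, and state that it cannot accept or reject the 8.2 hypothesis.
- **Description:** report the median and IQR of the paired log2 ratio as well as the separate medians at each time.

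The cost is plan wording and short exact calculations; no patient, scan or procedure changes. Two things are given up: a significant signed-rank result can no longer be presented as a primary success, and the 80% power claim for Cohort 1 at 12 patients goes.
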